### **8.4.3 Unexpected Adverse Events**

The Investigator Brochure contains the Reference Safety Information (RSI) which will be used for assessing expectedness. If an event is not listed in the RSI, it should be considered unexpected or if the AE occurs at a greater severity, specificity or frequency, it should be considered unexpected.

### **8.4.4 Eliciting adverse event information**

The Investigator is to report all directly observed AEs and all AEs spontaneously reported by the study subject. In addition, each study subject will be questioned about AEs at each scheduled clinic visit after study drug administration or during any telephone contact with the subject. The type of question asked should be open-ended, for example, *“How have you been feeling?”* or a similar type of query.

### **8.4.5 Recording Serious and Non-serious Adverse Events**

All AEs (both serious and non-serious) that occur in subjects during the AE reporting period must be recorded, whether or not the event is considered drug related. In addition, any known untoward event that occurs subsequent to the AE reporting period that the Investigator assesses as possibly related to the investigational drug/product should also be recorded as an AE.

All AEs are to be recorded in the source documents and on the eCRF using concise medical terminology; whenever possible, terms contained in the Medical Dictionary for Regulatory Activities (MedDRA) should be employed. In addition, the following information should be recorded:

1. Indication of whether the event is serious or non-serious (see Section [8.4.2](#))
2. Relationship to study drug (see Section [8.4.2](#))
3. Severity of the event (see Section [8.4.7](#))
4. Onset date
5. Resolution date, or date of death
6. Action taken
7. Outcome of the event

Classification of the event as serious or non-serious determines the reporting procedures to be followed.

### **8.4.6 Describing adverse event relationship to study drug**

The Investigator should provide an assessment of the relationship of the AE to the study drug, ie, whether there is a reasonable possibility that the study drug caused the AE, using the considerations outlined in [Table 7](#).

**Table 7. Relationship of Study Drug to Adverse Event Relationship**

Relationship	Description
Probable	A clinical event in which a relationship to the study drug seems probable because of such factors as consistency with known effects of the drug; a clear temporal association with the use of the drug; improvement upon withdrawal of the drug; recurrence upon rechallenge with the drug; lack of alternative explanations for the event.
Possible	A clinical event occurring coincident with administration of the study drug and which may or may not be explained by concurrent disease or other drugs or chemicals. Information on drug withdrawal or rechallenge may be lacking.
Unlikely	A clinical event with a temporal relationship to the study drug exposure that does not preclude causality but for which there is a clear alternate cause that is more likely to have caused the adverse event than study drug. Such alternatives include a concomitantly administered drug, the subject's disease state, other medical conditions, or environmental factors.
Unrelated	A clinical event, for which a relationship to the study drug seems improbable because of factors such as inconsistency with known effects of the study drug, lack of a temporal association with study drug administration, lack of association of the event with study drug withdrawal or rechallenge, and/or presence of alternative explanations for the event. Alternative explanations might include a known relationship of the adverse event to a concomitant drug, medical history of a similar event, the subject's disease state, other medical conditions, or environmental factors.

#### 8.4.7 Grading of Severity of Adverse Event

The severity of AE will be graded using the Common Terminology Criteria for Adverse Events (CTCAE) Version 5.0 (refer to the Study Manual). For each episode, the highest severity grade attained should be reported.

If a CTCAE criterion does not exist, the Investigator should use the grade or adjectives: Grade 1 (mild), Grade 2 (moderate), Grade 3 (severe), Grade 4 (life-threatening), or Grade 5 (fatal) to describe the maximum intensity of the AE. For purposes of consistency with the CTCAE, these intensity grades are defined in Table 8.

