8. A preexisting condition (eg, allergic rhinitis) must be noted on the appropriate eCRF for Visit 1 but should not be reported as an AE unless the condition worsens, or episodes increase in frequency during the AE reporting period. Diagnostic and therapeutic noninvasive and invasive procedures, such as surgery, should not be reported as AEs. However, the medical condition for which the procedure was performed should be reported if it meets the definition of an AE. For example, an acute appendicitis that occurs during the treatment with study drug should be reported as the AE and the resulting appendectomy should be recorded in the source documents and eCRF. If a surgical procedure was planned prior to entry into the study, and the surgery is not performed because of a worsening of a baseline condition, this should not be reported as an AE. Note that, as described in Section 8.4.2 any hospitalization occurring as the consequence of an AE during the study period should be reported as an serious adverse event (SAE).

Each AE is to be classified as serious or non-serious by the Investigator using medical and scientific judgment.

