**Table 9. Investigator Site Requirements for Reporting Adverse Events**

Event	Recorded on the eCRF	Reported on the SAE Report Form to PTC Pharmacovigilance Within 24 Hours of Awareness
Serious AE	All	All
Non-Serious AE	All	None
Exposure to the study drug during pregnancy or breastfeeding, and occupational exposure	All (regardless of whether associated with an AE), except occupational exposure	Exposure during pregnancy, exposure via breastfeeding, occupational exposure (regardless of whether associated with an AE)

**Abbreviations:** AE, adverse event; eCRF, electronic case report form; SAE, serious adverse event  
All AEs should be followed up by the Investigator until they are resolved, or the Investigator assesses them as chronic or stable. The Investigator should consider protocol guidelines and use his/her discretion in ordering additional tests as necessary to monitor the resolution of such events. In the event of additional investigations, the PTC Therapeutics Pharmacovigilance Department or designee should be informed via e-mail or fax. A subject withdrawn from the study because of an AE must be followed by the Investigator until clinical recovery is complete and laboratory results have returned to normal, or until progression has been stabilized. Follow-up may need to continue after the subject has discontinued from the study, and additional investigations may be requested by the PTC Therapeutics medical monitoring team.

The first day of AE reporting will coincide with the date of signing of informed consent and including a minimum of 30 calendar days after the last administration of study drug.

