### **9.5.7.1 Adverse Events**

Adverse events will be classified as pre-treatment adverse event, treatment-emergent adverse event (TEAE) and post-treatment adverse event. Pre-treatment AE is defined as the AE occurring or worsening prior to the start of the study treatment. TEAE is defined as the AE occurring or worsening on or after the first study dose and up to 30 days after the last study dose. Post-treatment AE is defined as the AE occurring or worsening after 30 days of the last study dose.

Adverse events will be coded using the most recent version of MedDRA. The severity of AEs will be graded by investigators according to the CTCAE, Version 5.0 whenever possible.

The frequency of subjects experiencing a specific adverse event will be tabulated by system organ class (SOC) and preferred term (PT). AE leading to study medication discontinuation, AE leading to dose reduction/interruption, AE related to study medication, AE leading to death, AEs with CTCAE Grade 3 or higher, and SAE will be tabulated and summarized by treatment by SOC and PT.

If a subject experience the same preferred term multiple times, the event will be counted only once and by the greatest severity.

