6.12 Safety Analyses

The safety analyses will be presented for the Safety Population.

The adverse events and other safety summaries will be reported across all deflazacort treated periods. The adverse events occurred during placebo period for subject randomized to placebo under protocol version 3.0 will not be summarized and will only be included in by-subject listings.

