6.12.1 Adverse Events

Adverse events (AEs) will be classified as pre-treatment adverse event, treatment-emergent adverse event (TEAE) and post-treatment adverse event. Pre-treatment AE is defined as the AE occurring prior to the start of the deflazacort treatment.

TEAE is defined as the AE occurring or worsening on or after the first deflazacort dose and up to 30 days after the last deflazacort dose. Post-treatment AE is defined as the AE occurring after 30 days of the last deflazacort dose.

If a subject experience the same preferred term multiple times, the event will be counted only once and by the greatest severity.

TEAEs will be summarized by System Organ Class (SOC) and Preferred Term (PT) according to the Medical Dictionary for Regulatory Activities (MedDRA, version 23.1).

A treatment-related AE is defined as an AE as being possibly or probably related to the study drug. If an AE has a missing relationship it is assumed to be related to the study drug for analysis purposes.

An overall TEAE summary table will be provided with following information:

- The number of subjects with at least one TEAE
- The number of subjects with at least one treatment related TEAE
- The number of subjects with at least one Grade 3 or Grade 4 TEAE
- The number of subjects with a Grade 5 TEAE (Fatal)
- The number of subjects with at least one SAE
- The number of subjects with at least one TEAE leading to treatment discontinuation

QMD Ref: Worldwide-TMP-ST-005-7.0 Effective: 12Aug2019	Governing QMD: Worldwide-SOP-ST-001
Confidentiality Statement	
This document is the property of Worldwide Clinical Trials Inc. and may not be duplicated, copied, altered or removed from company without prior approval from Worldwide Quality Assurance or in compliance with Worldwide Standard Operating Procedures.	

Worldwide Clinical Trials Controlled Quality Management Document		
 WORLDWIDE CLINICAL TRIALS	Sponsor:	PTC Therapeutics, Inc
	Protocol Number:	PTCEMF-GD-004
STATISTICAL ANALYSIS PLAN		

- The number of subjects with at least one TEAE leading to dose reduction or interruption

In addition, the All TEAE by SOC and PT summary tables will be provided.

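### With one highest grade and one onset date per AE, the documents cannot show whether an AE already open at first deflazacort worsened on it, so its TEAE status can err either way

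*Protocol*

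**What the plan says.** **Capture.** AE recording starts at consent: "The first day of AE reporting will coincide with the date of signing of informed consent" (Protocol, text under Table 9). Protocol 8.4.5 lists what is recorded for each event: seriousness, relationship, severity, an onset date, "Resolution date, or date of death", action taken and outcome. On severity, Protocol 8.4.7 says "For each episode, the highest severity grade attained should be reported". Neither section asks for the date of a grade change or for the grade at first dose.

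**Classification.** SAP 6.12.1 says "TEAE is defined as the AE occurring or worsening on or after the first deflazacort dose", with a limit of 30 days after the last dose. The same section says "Pre-treatment AE is defined as the AE occurring prior to the start of the deflazacort treatment". It does not say which class applies when an AE fits both. Protocol 9.5.7.1 words its rule in the same way but anchors it to the first study dose: "TEAE is defined as the AE occurring or worsening on or after the first study dose".

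**Placebo period.** SAP 6.12 says "The adverse events occurred during placebo period for subject randomized to placebo under protocol version 3.0 will not be summarized"; those events go to by-subject listings.

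**Worsening of earlier conditions.** Protocol 8.4.1 item 4 counts worsening of a preexisting illness as reportable. Item 8 says that a preexisting condition noted at Visit 1 "should not be reported as an AE unless the condition worsens, or episodes increase in frequency during the AE reporting period".

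**Missing stop date.** SAP Appendix 1 treats an AE whose stop date is entirely missing as a TEAE. That sentence sets no condition on the start date.

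**The concern.** The TEAE definition has two arms, starting and worsening. The first needs an onset date, which is recorded. The second needs a grade before first deflazacort and a later, higher grade with a date, and the listed fields hold neither.

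The SAP anchors the definition to first deflazacort, so for former placebo subjects the whole placebo phase is pre-treatment time. That makes the worsening arm most important for them. A condition that is Grade 1 on placebo and Grade 3 on deflazacort may be stored as one Grade 3 record with a placebo-period onset.

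The TEAE tables matter because little else in safety is summarised. SAP 6.12.2 to 6.12.6 and section 9 put laboratory, vital-sign, ECG, physical and ophthalmology results in listings only. An analyst also cannot recover the missing grade or date from the dataset afterwards.

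**Working it through.** The plan gives no figure for this point, so there is none to reproduce. The check applies the written rules to AE patterns and then sizes one misclassification.

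**Step 1: patterns.** Take one AE that starts on day −10 relative to first deflazacort and is held as a single record with its highest grade. The days are illustrative.

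| Course after first deflazacort | SAP 6.12.1 definition | Classified by start date only | Same, plus Appendix 1 missing-stop rule read literally | New record opened at worsening |
|---|---|---|---|---|
| A: worsens day 15, resolves day 40 | TEAE | not TEAE | not TEAE | TEAE |
| B: worsens day 15, no stop date | TEAE | not TEAE | TEAE | TEAE |
| C: never worsens, no stop date | not TEAE | not TEAE | TEAE | not TEAE |
| D: never worsens, resolves day 40 | not TEAE | not TEAE | not TEAE | not TEAE |

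The last column assumes that the missing-stop rule no longer captures C.

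**Step 2: what the record can distinguish.** A and D have the same start date and the same stop date. If D reached its highest grade before deflazacort and A reached the same grade after it, the severity and date fields are identical, yet the definition puts them in different classes. The same holds for B and C. No programming rule on these fields can separate them: a rule that gets D right gets A wrong, and the missing-stop rule that gets B right gets C wrong. C can also carry a grade reached before deflazacort.

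**Step 3: do the reporting rules close the gap?** Item 8 of Protocol 8.4.1 concerns conditions noted at Visit 1. For a former placebo subject, Visit 1 precedes placebo, so an AE that begins on placebo is not clearly covered. Item 4 makes worsening of a preexisting illness reportable but does not say that worsening of an AE already on file starts a new record.

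**Step 4: exposure to the problem.** The screening window is up to 6 weeks (Schedule of Events). The placebo period is nominally up to 26 weeks, so pre-deflazacort AE time is up to about 6 + 26 = 32 weeks for a former placebo subject. It is shorter for those accelerated to the Week 26 visit under Protocol 3.4.

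**Step 5: size.** SAP section 1 gives 11 subjects enrolled. If all 11 received deflazacort, one subject is 1/11 = 9.1 percentage points, two are 2/11 = 18.2 and three are 3/11 = 27.3. These are the most that an incidence row can move. The change for a subject is zero if that subject already has another TEAE that qualifies for the row. If fewer were dosed, one subject weighs more; with 10 dosed, for example, 1/10 = 10.0 points.

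**The case against.** The strongest reply is that the SAP contains no instruction to lose these events. A Grade 1 AE that becomes Grade 3 on deflazacort meets the TEAE definition as written, and nothing says to classify on onset date alone or lets the pre-treatment class override. This stands. A reader might infer that such AEs automatically fall out of the TEAE tables, but the documents do not support that. It follows only for AEs that resolve with a stop date, have no new record at worsening and are classified by start date.

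A reader might also infer that the error always flatters deflazacort. Appendix 1 rules that out: pattern C adds events. The literal reading of that rule may not be the intended one. The appendix says its rules yield to contrary eCRF data, and it later gives a separate rule for AEs with both dates missing. But a known early start does not by itself contradict emergence by worsening, so the ambiguity remains.

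Third, the eCRF, its guidelines and the Study Manual are not in the documents. They may require a new record at worsening or collect grade changes, and the protocol does not define an episode. Items 4 and 8 of 8.4.1 can reasonably cover many screening-period conditions. This stands as a limit on certainty.

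Finally, the study is small, tests no hypothesis (Protocol 9.1) and lists all AEs by subject (SAP 6.12.1). That limits the harm. It does not repair the record, because a listing of the same fields also shows only the onset date and highest grade.

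**Conclusion.** The point holds as a gap in capture and classification. For an AE open at first deflazacort, chiefly one that began in the placebo period, the fields listed in Protocol 8.4.5 and 8.4.7 do not allow the worsening arm of the SAP 6.12.1 definition to be derived, and no stated rule settles the class. A resolved AE that worsened can be omitted from the TEAE tables with its worst grade listed under placebo. An unresolved AE that never worsened can be counted.

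The size is 0 or about 9 percentage points per affected subject per incidence row, assuming that all 11 were dosed. A reader might take 9 points as a minimum for each misclassified subject; it is not, because a subject with another qualifying TEAE changes nothing in that row. The documents give neither the number of AEs open at first deflazacort nor the number of former placebo subjects, so no total effect can be stated. The conclusion assumes that the unseen eCRF guidelines add no rule on worsening; if they do, the remaining issue is the SAP wording.

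**What to change.** 1. Before database lock, query every AE open at first deflazacort. Where it later worsened, record the worsening as a new AE with its own onset date and grade, and keep the pre-deflazacort record at the grade it had reached by then. If the eCRF guidelines already require this, confirm that it was done.
2. In SAP 6.12.1, state that an AE that worsens on or after first deflazacort is a TEAE even if it began earlier, so that this class takes precedence over pre-treatment.
3. In SAP Appendix 1, limit the missing-stop-date rule to AEs that start or worsen on or after first deflazacort, or whose start cannot be placed before it.

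All three are needed: new records alone would leave pattern C counted as a TEAE. The cost is a short set of queries on at most 11 subjects and two sentences in the SAP. The downside is that one continuing condition may appear as two records. In the TEAE tables this matters little, since SAP 6.12.1 counts a preferred term once per subject. The documents do not give the lock date; if lock has passed, a footnote to the TEAE tables and AE listings should identify the AEs that were open at first deflazacort.

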**Table 8. Grading of Adverse Event Severity Grade**

	Adjective	Description
Grade 1	Mild	Sign or symptom is present, but it is easily tolerated, is not expected to have a clinically significant effect on the subject's overall health and well-being, does not interfere with the subject's usual function, and is not likely to require medical attention
Grade 2	Moderate	Sign or symptom causes interference with usual activity or affects clinical status, and may require medical intervention
Grade 3	Severe	Sign or symptom is incapacitating or significantly affects clinical status and likely requires medical intervention and/or close follow-up
Grade 4	Life-threatening	Sign or symptom results in a potential threat to life
Grade 5	Fatal	Sign or symptom results in death

### 8.4.8 Adverse Event Reporting

Investigator site reporting requirements for AEs are summarized in Table 9.

**Table 9. Investigator Site Requirements for Reporting Adverse Events**

Event	Recorded on the eCRF	Reported on the SAE Report Form to PTC Pharmacovigilance Within 24 Hours of Awareness
Serious AE	All	All
Non-Serious AE	All	None
Exposure to the study drug during pregnancy or breastfeeding, and occupational exposure	All (regardless of whether associated with an AE), except occupational exposure	Exposure during pregnancy, exposure via breastfeeding, occupational exposure (regardless of whether associated with an AE)

**Abbreviations:** AE, adverse event; eCRF, electronic case report form; SAE, serious adverse event  
All AEs should be followed up by the Investigator until they are resolved, or the Investigator assesses them as chronic or stable. The Investigator should consider protocol guidelines and use his/her discretion in ordering additional tests as necessary to monitor the resolution of such events. In the event of additional investigations, the PTC Therapeutics Pharmacovigilance Department or designee should be informed via e-mail or fax. A subject withdrawn from the study because of an AE must be followed by the Investigator until clinical recovery is complete and laboratory results have returned to normal, or until progression has been stabilized. Follow-up may need to continue after the subject has discontinued from the study, and additional investigations may be requested by the PTC Therapeutics medical monitoring team.

The first day of AE reporting will coincide with the date of signing of informed consent and including a minimum of 30 calendar days after the last administration of study drug.

### 8.4.9 Serious Adverse Event Reporting

All SAEs should be reported via the SAE report form to PTC Therapeutics within 24 hours of becoming aware of the event(s). In addition, the AE portion of the eCRF must also be completed.

The SAE report form should be signed by the Investigator; however, if the Investigator is unable to sign at the time of the event or within 24 hours, the form should be signed by the clinical staff member reporting the SAE (eg, the study coordinator). The SAE report form must be faxed or e-mailed to the PTC Therapeutics Pharmacovigilance Department or designee and to the site Institutional Review Board/Institutional Ethics Committee (IRB/IEC) (if required by local regulations) within 24 hours.

Follow-up information to the SAE should be clearly documented as “follow-up” in the SAE report form and must also be faxed or e-mailed to the same party. All follow-up SAE report forms for the event must be signed by the Investigator. Any source documents (eg, progress notes, nurses’ notes, laboratory and diagnostic test results, discharge summaries) provided to the sponsor should be redacted so that the subject’s name, address, and other personal identity information are obscured. Only the subject’s study number and initials are to be provided (in regions where the provision of such information is permitted). The information in the AE portion of the eCRF and the SAE report form(s) must match or be reconciled. Where the same data are collected, the forms must be completed in a consistent manner. For example, the same AE term should be used on both forms.

In the rare event that the Investigator does not become aware of the occurrence of an SAE immediately (for example, if a subject initially seeks treatment elsewhere), the Investigator is to report the event within 24 hours after learning of it and to document his/her first awareness of the AE.

The PTC Therapeutics Pharmacovigilance Department contact information for reporting SAEs is provided below. This information is also provided in the Study Manual and in the SAE report form.

